5.3 Maintenance Therapy

5.3.1 Randomization

Following completion of consolidation therapy, patients will undergo restaging and will be randomized on a 1:1 basis to maintenance therapy with ixazomib (Arm1) or lenalidomide (Arm2). Patients will be stratified based on MRD status at restaging (MRD-positive vs. MRD-negative). To better ensure the balance of patient characteristics across two arms, treatment assignment will be implemented in small blocks of 4 to 6 patients. The randomization table will be uploaded in our REDCap system. Randomization will occur via an online form with entry of the patient ID number and stratum information. Once all information is entered, randomization is carried out via a submit button through REDCap. The randomization scheme will be created using a formal probability model implemented in SAS (version 9.3 or higher).

5.3.2 Ixazomib Administration

Ixazomib will be prescribed only to eligible patients under the supervision of the investigator or identified sub-investigator(s). Ixazomib will be administered on Days 1, 8, and 15 of a 28-day cycle at a starting dose of 4 mg. Sufficient quantity of drug for one cycle of therapy will be prescribed to the patient in Cycles 1-3 of maintenance therapy, and for three cycles of therapy in Cycles 4+.

Patients should be monitored for toxicity, as necessary, and doses of ixazomib should be modified as needed to accommodate patient tolerance to treatment; this may include symptomatic treatment, dose interruptions, and adjustments of ixazomib dose (see Section 6.0). Once ixazomib is reduced for toxicity, no dose re-escalation is permitted.

Ixazomib should be taken on an empty stomach (no food or drink), at least 1 hour before or 2 hours after a meal. Patients should be instructed to swallow ixazomib capsules whole and not to break, chew, or open the capsules. Each capsule should be swallowed separately with a sip of water. A total of approximately 8 ounces (240 mL) of water should be taken with the capsules.

Ixazomib should be taken at the same time each day. Missed doses can be taken as soon as the patient remembers if the next scheduled dose is 72 hours or more away. A double dose should not be taken to make up for a missed dose. Patients who vomit a dose after ingestion will not receive an additional dose, but should resume dosing at the time of the next scheduled dose.

If ixazomib maintenance is discontinued, crossover to the lenalidomide maintenance arm can occur if permission is granted by the Principal Investigator. Patients who crossover will continue to be followed per all protocol guidelines.

5.3.3 Lenalidomide Administration

Lenalidomide will be prescribed only to eligible patients under the supervision of the investigator or identified sub-investigator(s). Lenalidomide will be administered daily continuously for a 28-day cycle at a starting dose of 10 mg. If lenalidomide is tolerated well (i.e. no dose modification required) during the first three cycles, lenalidomide dose will be increased to 15 mg daily. Sufficient quantity of drug for one cycle of therapy will be prescribed to the patient in Cycles 1-3, and for three cycles of therapy in Cycles 4+. Lenalidomide will be provided in accordance with the Celgene Corporation's Revlimid REMS® program.

VTE prophylaxis is not required during single-agent lenalidomide maintenance but is permissible at the discretion of the treating physician.

Patients should be monitored for toxicity, as necessary, and doses of lenalidomide should be modified as needed to accommodate patient tolerance to treatment; this may include symptomatic treatment, dose interruptions, and adjustments of lenalidomide dose (see Section 6.0).

If a lenalidomide dose reduction has occurred for hematologic toxicity and ANC $>1000/\mu\text{L}$ and platelet count is $>75,000/\mu\text{L}$, lenalidomide drug dose may be re-escalated one dose level per cycle to a maximum of 15 mg daily. If lenalidomide was reduced due to non-hematologic toxicity, no dose re-escalation is permitted.

Lenalidomide can be taken without regards to food or drink. Patients should be instructed to swallow lenalidomide capsules whole and not to break, chew, or open the capsules. Each capsule should be swallowed separately with a sip of water.

Lenalidomide should be taken at the same time each day. Missed doses can be taken as soon as the patient remembers if the next scheduled dose is 8 hours or more away. A double dose should not be taken to make up for a missed dose. Patients who vomit a dose after ingestion will not receive an additional dose, but should resume dosing at the time of the next scheduled dose.

If lenalidomide maintenance is discontinued, crossover to the ixazomib maintenance arm can occur if permission is granted by the Principal Investigator. Patients who crossover will continue to be followed per all protocol guidelines.

5.4 Excluded Concomitant Medications and Procedures

Systemic treatment with any of the following metabolizing enzyme inducers should be avoided in this study (14 days before the 1st dose of ixazomib until the final dose of ixazomib), unless there is no appropriate alternative medication for the patient's use. (Rationale: Unlike with inhibitors, if there were to be a DDI with an inducer, ixazomib exposure would be less; therefore, there would be a reduced chance of an AE. However, there may be less chance for an antitumor effect, but that is not an absolute reason to be taken off ixazomib.)

- Strong CYP3A inducers: rifampin, rifapentine, rifabutin, carbamazepine, phenytoin, and phenobarbital
- Excluded foods and dietary supplements include St. John's wort and Ginkgo biloba

The following procedures are prohibited during the study.

- Any antineoplastic treatment with activity against MM, other than study drugs
- Radiation therapy (note that, in general, the requirement for local radiation therapy indicates disease progression)
- Platelet transfusions to help patients meet eligibility criteria are not allowed within 3 days prior to study drug dosing for any dosing day

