Metabolism appears to be the major route of elimination for ixazomib, and urinary excretion of the parent drug is negligible (< 5% of dose). In vitro studies indicate that ixazomib is metabolized by multiple cytochrome P450s (CYPs) and non-CYP enzymes/proteins. The rank order of relative biotransformation activity of the 5 major human CYP isozymes was 3A4 (34.2%) > 1A2 (30.7%) > 2D6 (14.7%) > 2C9 (12.1%) > 2C19 (< 1%). Ixazomib is not an inhibitor of CYPs 1A2, 2C9, 2C19, 2D6, or 3A4 nor a time-dependent inhibitor of CYP3A4/5. The potential for ixazomib treatment to produce drug-drug interactions (DDIs) via CYP inhibition is inferred to be low. However, there may be a potential for DDIs with a concomitant strong CYP3A4 or CYP1A2 inhibitor or inducer because of the potential for first-pass metabolism when ixazomib is administered via the PO route and because of the moderate contribution of CYP3A4- and CYP1A2-mediated metabolism of ixazomib in human liver microsomes. Ixazomib may be a weak substrate of P-glycoprotein (Pgp), breast cancer resistance protein (BCRP), and multidrug resistance associated protein (MRP2) efflux pump transporters. Ixazomib is not an inhibitor of Pgp, BCRP, and MRP2. The potential for DDIs with substrates or inhibitors of Pgp, BCRP, and MRP2 is, therefore, inferred to be low. Clinical Study C16009 (Arm 1) with ketoconazole, a strong CYP3A4 inhibitor, showed a 2-fold increase in area under the plasma concentration versus time curve (AUC) in the presence of ketoconazole. This resulted in the continued exclusion of strong CYP3A4 inhibitors in ongoing/planned clinical studies.

Further details on these studies are provided in the IB.

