5.5 Permitted Concomitant Medications and Procedures

The following medications and procedures are permitted during the study:

- Antiemetics, including 5-HT₃ serotonin receptor antagonists, may be used at the discretion of the investigator.
- Loperamide or other antidiarrheal should be used for symptomatic diarrhea at discretion of the investigator. The dose and regimen will be according to institutional guidelines. IVF should be given to prevent volume depletion.
- Growth factors (e.g., granulocyte colony stimulating factor [G-CSF], granulocyte macrophage-colony stimulating factor [GM-CSF], recombinant erythropoietin) are permitted, but should not be given prophylactically. Their use should follow published guidelines and/or institutional practice; however, alternative usage may be reviewed with the principal investigator.
- Patients should be transfused with red cells and platelets as clinically indicated and according to institutional guidelines.
- Antiviral therapy such as acyclovir may be administered if medically appropriate.
- Concomitant treatment with bisphosphonates will be permitted, as appropriate.
- Patients who experience worsening neuropathy from baseline may be observed for recovery, have dose reductions/delays as indicated in the protocol, and any supportive therapy or intervention may be initiated as appropriate at the discretion of the investigator.
- Supportive measures consistent with optimal patient care may be given throughout the study.

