6.2 Criteria for Beginning a New Treatment Cycle

For a new cycle of treatment to begin, the patient must meet the following criteria:

- ANC must be $\geq 1,000/\text{mm}^3$.
- Platelet count must be $\geq 75,000/\text{mm}^3$.
- All other treatment related non-hematologic toxicity (except for alopecia) must have resolved to \leq Grade 1 or to the patient's baseline condition

If the patient fails to meet the above-cited criteria for initiation of the next cycle of treatment, dosing should be delayed for 1 week. At the end of that time, the patient should be re-evaluated to determine whether the criteria have been met. If the criteria have been met, resume at previous dose levels.

If the patient continues to fail to meet the above-cited criteria, delay therapy and continue to re-evaluate weekly. If a delay of > 2 weeks is required, reduce the suspected drug(s) by one dose level when treatment is resumed. Dosing adjustments should not occur in both ixazomib and lenalidomide simultaneously.

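### Section 5.4 restricts CYP3A inducers but not strong CYP3A4 inhibitors, although Section 1.2.3 reports that one doubled ixazomib AUC and that the class stays excluded in ixazomib studies

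*Combined protocol and SAP*

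**What the plan says.** Section 1.2.3 treats both directions of metabolic interaction as possible: "there may be a potential for DDIs with a concomitant strong CYP3A4 or CYP1A2 inhibitor or inducer". It then gives one result. Study C16009 (Arm 1) "showed a 2-fold increase in area under the plasma concentration versus time curve (AUC) in the presence of ketoconazole", and the consequence drawn is "This resulted in the continued exclusion of strong CYP3A4 inhibitors in ongoing/planned clinical studies". The section refers to the Investigator's Brochure for further detail.

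Section 5.4 is the list that sites act on. Its opening rule on interactions is "Systemic treatment with any of the following metabolizing enzyme inducers should be avoided in this study", from 14 days before the first ixazomib dose to the last, "unless there is no appropriate alternative medication". The drugs named are six strong CYP3A inducers, plus two supplements. Inhibitors appear only as a contrast in the rationale: "Unlike with inhibitors, if there were to be a DDI with an inducer, ixazomib exposure would be less".

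Section 5.5 adds a broad permission: "Supportive measures consistent with optimal patient care may be given throughout the study". It sets no limit on enzyme inhibitors.

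**The concern.** The background and the operative text do not agree. Section 1.2.3 identifies strong CYP3A4 inhibitors as the drugs with a measured effect on ixazomib exposure and says that they stay excluded across the programme. Section 5.4 restricts the opposite class, and justifies a lenient rule for it partly because lower exposure means fewer adverse events. That reasoning implies that inhibitors are the larger safety concern, yet 5.4 has no rule for them.

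A site that follows 5.4 and 5.5 exactly could prescribe a strong CYP3A4 inhibitor alongside ixazomib without a protocol deviation. What is at stake is avoidable over-exposure in individual patients.

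**Working it through.** The plan states no figure to reproduce, so the check is a comparison of texts plus a count of the doses in scope.

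**Step 1: the two sections side by side.**

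| | Section 1.2.3 | Section 5.4 |
|---|---|---|
| Strong CYP3A4 inhibitors | Possible interaction; 2-fold AUC with ketoconazole; exclusion continues in ongoing and planned studies | Not listed; mentioned only as a contrast |
| Strong CYP3A inducers | Possible interaction | To be avoided, with an exception |
| Strong CYP1A2 inhibitors or inducers | Possible interaction; no exclusion stated | Not listed |

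**Step 2: is the inhibitor rule somewhere else?** The eligibility criteria (3.1, 3.2), drug administration (5.2, 5.3), permitted medications (5.5), dose modifications (6.0 to 6.4) and management of clinical events (6.5) contain no restriction, caution or dose adjustment for CYP3A4 inhibitors.

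**Step 3: do later safeguards fill the gap?** They detect and manage toxicity; they do not prevent the interaction.
- Section 6.2 sets a check before each cycle: "For a new cycle of treatment to begin, the patient must meet the following criteria", covering neutrophils, platelets and non-hematologic toxicity.
- In consolidation, the first listed response to grade 3 thrombocytopenia (6.3.1) lowers lenalidomide, not ixazomib. Section 6.0 does allow alternative modifications.
- If toxicity leads to an ixazomib reduction, 5.2.1 and 5.3.2 do not allow re-escalation. One level is (4.0 − 3.0)/4.0 = 25%, and it stays in place even if the inhibitor was taken only briefly.
- From maintenance Cycle 4 the study calendar places blood counts on Day 1 of every third cycle. Up to 3 cycles × 3 doses = 9 ixazomib doses can fall between calendar counts, although 6.2 still sets count thresholds for every cycle.

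**Step 4: doses in scope.** Consolidation plans 4 cycles × 3 doses = 12 ixazomib doses for each of about 240 patients. Ixazomib maintenance adds 3 per cycle in an arm planned at 110 evaluable patients. These are denominators only. The documents do not say how many patients would need a strong inhibitor, so no expected number of affected doses can be given.

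**The case against.** The strongest reply is that the omission may be deliberate. Section 1.2.3 is a programme-level summary that does not name this trial. The clinical data in Section 1.2 are dated 27 March 2013, while 1.2.9 reports a November 2015 approval. The exclusion may have been lifted in between, and the brochure that would settle this is not among the documents. This stands, and it is why the exclusion has to be conditional on the current brochure. It does not remove the inconsistency: if inhibitors are now acceptable, 1.2.3 is out of date and 5.4 should say so. Until then, exclusion is the only position on inhibitors that the protocol states.

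Second, partial protections exist. Exclusion criterion 15 bars infection requiring systemic antibiotics within 14 days before treatment, and Sections 5.2.1 and 5.3.2 call for toxicity monitoring with dose interruption as needed. These narrow the practical gap, but the first applies only at entry and none is a rule on inhibitors.

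Two stronger readings are tempting.
- A reader might infer that 4 mg taken with a strong inhibitor acts like 4 × 2 = 8 mg, above the weekly maximum tolerated dose in C16005 (2.97 mg/m², about 5.5 mg by the Table 1-1 footnote). That needs exposure proportional to dose, which the documents do not state, and it would not measure expected harm.
- A reader might carry the 14-day inducer window over to inhibitors and hold ixazomib only while the inhibitor is taken. Nothing in the documents supports that window for inhibitors. With a terminal half-life of about 5 to 7 days (1.2.3), skipping the next weekly dose does not remove drug already taken.

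**Conclusion.** The inconsistency is real and should be fixed. The protocol restricts the drugs that lower ixazomib exposure and is silent on those that its own background says raise it 2-fold. No other section makes good the omission.

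The conclusion rests on the text alone. It does not show that the omission was a mistake, that any patient was harmed, or how often strong inhibitors would be used. A reader might also infer a threat to the primary result. The documents do not support that: the gap shows no error in the McNemar comparison, the power calculation or the alpha. This is a matter of patient safety and internal consistency.

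**What to change.** In Section 5.4:
- widen the lead-in so that it no longer covers inducers alone;
- list strong CYP3A4 inhibitors as drugs to be avoided while on ixazomib;
- give them their own rationale, namely higher exposure and the 2-fold AUC with ketoconazole;
- where one is unavoidable, have the principal investigator decide whether to hold ixazomib, with washout and timing taken from the current Investigator's Brochure.

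If that brochure no longer supports exclusion, correct 1.2.3 instead and state in 5.4 that inhibitors are permitted and why. The same edit can settle whether strong CYP1A2 inhibitors need a rule, since 1.2.3 names them as a possible interaction.

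The drafting is a few lines, sent to the local IRBs by the route in Section 16.0. For patients, a few would need another medicine or an ixazomib interruption. A 3-week interruption spans up to 3 of 12 consolidation doses (3/12 = 25%) if they are not made up. Beyond 3 weeks, Section 6.0 calls for discontinuation unless the principal investigator permits resumption, and 15.3 limits the consolidation efficacy analysis to patients who complete four cycles. A long interruption could therefore cost a patient evaluability. The accrual plan leaves about 240 − 220 = 20 patients for non-evaluability from all causes.

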5.5 Permitted Concomitant Medications and Procedures

The following medications and procedures are permitted during the study:

- Antiemetics, including 5-HT₃ serotonin receptor antagonists, may be used at the discretion of the investigator.
- Loperamide or other antidiarrheal should be used for symptomatic diarrhea at discretion of the investigator. The dose and regimen will be according to institutional guidelines. IVF should be given to prevent volume depletion.
- Growth factors (e.g., granulocyte colony stimulating factor [G-CSF], granulocyte macrophage-colony stimulating factor [GM-CSF], recombinant erythropoietin) are permitted, but should not be given prophylactically. Their use should follow published guidelines and/or institutional practice; however, alternative usage may be reviewed with the principal investigator.
- Patients should be transfused with red cells and platelets as clinically indicated and according to institutional guidelines.
- Antiviral therapy such as acyclovir may be administered if medically appropriate.
- Concomitant treatment with bisphosphonates will be permitted, as appropriate.
- Patients who experience worsening neuropathy from baseline may be observed for recovery, have dose reductions/delays as indicated in the protocol, and any supportive therapy or intervention may be initiated as appropriate at the discretion of the investigator.
- Supportive measures consistent with optimal patient care may be given throughout the study.

5.6 Pregnancy Risks – Precautions and Restrictions

It is not known what effects ixazomib has on human pregnancy or development of the embryo or fetus. Therefore, female patients participating in this study should avoid becoming pregnant, and male patients should avoid impregnating a female partner. Non-sterilized female patients of reproductive age group and male patients should use effective methods of contraception through defined periods during and after study treatment as specified below.

Female patients must meet 1 of the following:

- Postmenopausal for at least 1 year before the screening visit, or
- Surgically sterile, or
- If they are of childbearing potential, agree to practice 2 effective methods of contraception from the time of signing of the informed consent form through 90 days after the last dose of study drug, or
- Agree to practice true abstinence, when this is in line with the preferred and usual lifestyle of the subject. (Periodic abstinence [e.g., calendar, ovulation,

symptothermal, post-ovulation methods] and withdrawal are not acceptable methods of contraception.)

Male patients, even if surgically sterilized (i.e., status postvasectomy) must agree to 1 of the following:

- Practice effective barrier contraception during the entire study treatment period and through 90 days after the last dose of study drug, or
- Agree to practice true abstinence, when this is in line with the preferred and usual lifestyle of the subject. (Periodic abstinence [e.g., calendar, ovulation, symptothermal, post-ovulation methods for the female partner] and withdrawal are not acceptable methods of contraception.)

The use of lenalidomide in pregnant females and nursing mothers has not been studied nor has the effect of the lenalidomide on human eggs and sperm. Lenalidomide is structurally related to thalidomide. Thalidomide is a known human teratogenic active substance that causes severe life-threatening birth defects. An embryofetal development study in animals indicates that lenalidomide produced malformations in the offspring of female monkeys who received the drug during pregnancy. The teratogenic effect of lenalidomide in humans cannot be ruled out. Therefore, a risk minimization plan to prevent pregnancy must be observed.

A woman of childbearing potential is defined as a sexually mature woman who: 1) has not undergone a hysterectomy or bilateral oophorectomy or 2) has not been naturally postmenopausal for at least 24 consecutive months. Women of childbearing potential are required to have a negative serum or urine pregnancy test within 10-14 days prior to and again no more than 24 hours before the first dose of lenalidomide. Women of childbearing potential are required to use two forms of contraception at the same time, including one highly effective method (i.e., intrauterine device, hormonal (birth control pills, injections, or implants), tubal ligation, partner's vasectomy) and one additional effective (barrier) method (i.e., latex condom, diaphragm, cervical cap), from the time of signing of the informed consent form through 90 days after the last dose of study drug. Male patients engaged in a sexual relationship with a woman of childbearing potential must agree to use a latex condom during sexual contact, even if he has had a successful vasectomy.

If a patient is suspected to be pregnant, both study drugs should be immediately discontinued. In addition a positive urine test must be confirmed by a serum pregnancy test. If it is confirmed that the patient is not pregnant, the patient may resume dosing.

